## 1. Protocol Summary

Full Title:	Prostate Cancer Comparative Outcomes of New Conceptual Paradigms for Treatment
Short Title:	PC CONCEPT
Principal Investigators:	[name] MPH; [name] MPH
Study Description:	This study will use a population-based cohort design to study men with newly diagnosed low- and intermediate-risk prostate cancer at high-volume centers in Southern California (SCa) and New York State (NYS). Complications of contemporary treatments for prostate cancer and quality of life outcomes, such as general health, urinary, sexual, and bowel function, cancer anxiety, and treatment regret will be compared and tracked over the course of this study.
Sample Size:	N= 3,657
Enrollment:	This study will enroll 2,378 subjects and screen up to 3,657 subjects.
Study Population:	Subjects will have pathologically-confirmed clinically localized prostate adenocarcinoma with National Comprehensive Cancer Network (NCCN) low (T1-T2a, Gleason 6, Grade Group 1, PSA <10 ng/mL) or intermediate risk (T2b-T2c or, Gleason 7, Grade Group 2 or 3 or PSA 10-20 ng/mL) at one of the selected hospitals in SCa and NYS. Subjects must also have a diagnosis date during the 18-month recruitment window.
Enrollment Period:	18 months
Study Design:	Prospective, observational
Description of Sites	Patient enrollment at 15 sites within SCa and NYS, identified through National Cancer Institute-sponsored Surveillance Epidemiology and End Results (SEER)
Study Duration:	01Oct2020 - 30Nov2023
Participant Duration:	12 months
Primary Objectives:	To measure the self-reported, overall and disease specific health related quality of life (HRQOL) prior to treatment, at 8 months, and 12 months following active surveillance (AS), SBRT, IMRT, PGA, and RP.

To define and compare the rate of adverse events following stereotactic body radiation therapy (SBRT), partial gland ablation (PGA), intensity modulated radiation therapy (IMRT) and radical prostatectomy (RP) among men recently diagnosed with low and intermediate risk prostate cancer.

Primary Endpoints:	Change from Baseline in Patient-Reported Quality of Life as Measured on EQ-5D-5L at 8 Months & 12 Months following Treatment
	Change from Baseline in Patient-Reported Urinary, Sexual, and Bowel Function as Measured on EPIC-26 at 8 Months & 12 Months following Treatment
	Change from Baseline in Ejaculatory Function as Measured on MSHQ-EjD at 8 Months & 12 Months following Treatment
	Change from Baseline in Patient-Reported Anxiety as Measured on MAX-PC at 8 Months & 12 Months following Treatment
	Assessment of Treatment Regret as Measured on Clark's Prostate Cancer Health Worry at 8 Months & 12 Months following Treatment
	Assessment of Adverse Events at 8 Months & 12 Months following Treatment by CTCAE v5.0
	Assessment of Cancer Recurrence at 8 Months & 12 Months following Treatment by Patient Medical Records

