### 1.1. Objectives

To measure the self-reported, overall and disease specific health related quality of life (HRQOL) prior to treatment, at 8 months, and 12 months following active surveillance (AS), SBRT, IMRT, PGA, and RP.

To define and compare the rate of adverse events following stereotactic body radiation therapy (SBRT), partial gland ablation (PGA), intensity modulated radiation therapy (IMRT) and radical prostatectomy (RP) among men recently diagnosed with low and intermediate risk prostate cancer.

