### 1.2 Hypotheses / Research Questions

PGA is associated with less reduction of urinary and sexual function compared to before treatment than both RP and IMRT. SBRT is associated with less reduction of urinary and sexual

function before treatment compared to RP and IMRT. SBRT will be associated with less reduction in bowel function compared to IMRT. PGA is associated with better overall quality of life at 12 months compared to AS.

PGA and SBRT are associated with fewer adverse events compared to RP and IMRT.

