### **3.2 Patient Questionnaires – Refer to Appendix A.**

#### **A. Administration**

- **Timing and Frequency** – Baseline questionnaires will be sent to eligible participants for study enrollment. Follow-up questionnaires at 8 months and 12 months will be sent to enrolled participants to ascertain treatment choice and obtain patient-reported outcomes following treatment.
- **Survey method**  
Eligible participants will be mailed a survey packet consisting of a paper copy of the survey, an introductory letter and information sheet, and a postage paid return envelope. In the letter the participant will be informed that, if he wishes, he may also complete the survey online and will be given a code and link to the online survey. All materials will be provided in Spanish and English to those participants with Spanish surnames. Interviewers contacting the men are bilingual.

A modified Dillman method will be used to increase response. This includes follow-up with telephone, mail, and offers of completion of the survey online or by telephone.

Specifically, if no response is received after 2 weeks, the study staff will telephone the participant to determine if he has any questions or concerns and to encourage him to complete the survey. At least 5 calls will be made on different days, times of the day (including evenings), and on weekends to reach the person. Additional follow-up efforts will include sending reminder postcards, re-mailing of the survey packet, sending a reminder letter with the link to the online survey, or offering to do the interview over the telephone.

- **Person Identifiers**

Patient identifiers obtained at the time of rapid case ascertainment will be used to link to the completed registry abstract. The registry variables to be linked to the cases will include: patient demographic data (age, date of birth, race, socio-economic status, quintile of census block of residence, marital status, birthplace), tumor data (PSA, stage, histology, grade, clinical and pathologic Gleason score, extension), treatment data (surgical code, radiation (type), dates of treatments, chemotherapy, and hormone therapy, PGA and AS).

B. Study Instruments – Refer to [Appendix A](#).

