##### **4.2 Inclusion Criteria**

To be included in the study, the participant will: (1) have pathologically-confirmed clinically localized prostate adenocarcinoma with Grade Group 1-2 (Gleason score 6 & 7) at one of the selected hospitals in SCa and NYS; (2) have a diagnosis date during the 18 month recruitment window; (3) speak either English or Spanish and; 4) agree to participate by completing the baseline questionnaire.

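### Three of the seven primary endpoints (EQ-5D-5L, MSHQ-EjD, MAX-PC) are changes from a baseline that the Baseline Survey never measures; comorbidity, height and weight are asked only at 8 months

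*Combined protocol and SAP*

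**What the plan says.** Section 1 (Protocol Summary, Primary Endpoints) lists seven endpoints. Four are changes from baseline. One is EPIC-26 urinary, sexual and bowel function. The other three are as follows.

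- General health status is the subject of the first, which the plan words as "Change from Baseline in Patient-Reported Quality of Life as Measured on EQ-5D-5L at 8 Months & 12 Months following Treatment".
- Ejaculation is handled apart from the EPIC-26 sexual items, and the second of the three therefore reads "Change from Baseline in Ejaculatory Function as Measured on MSHQ-EjD at 8 Months & 12 Months following Treatment".
- The third is the only psychological outcome among these four change scores, and its wording is "Change from Baseline in Patient-Reported Anxiety as Measured on MAX-PC at 8 Months & 12 Months following Treatment".

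The remaining endpoints, namely regret, adverse events and recurrence, are assessed at follow-up and need no baseline.

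Section 1.1 sets out to measure "overall and disease specific health related quality of life (HRQOL) prior to treatment", so overall as well as disease-specific quality of life is to be measured before treatment. Section 6.1 (Schedule of Trial Events) marks patient reported outcomes, Charlson comorbidity, height and weight at baseline, 8 months and 12 months.

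Section 8 fits a GEE to the patient-reported outcomes, adjusted for risk group, age, race, Charlson index and a baseline disease-specific score. The adverse-event model is a logistic regression whose covariates include BMI and Charlson. Section 3.2 refers to Appendix A for the study instruments.

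**The concern.** A change score needs the same instrument at both ends. If the baseline form lacks the instrument, the endpoint cannot be produced as defined, and someone must choose a replacement estimand and covariate set. Unless that is settled in advance, it will be settled after the data have been seen.

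The groups are self-selected, so the outcome's own pre-treatment value is a natural confounder to adjust for. Section 8 names only a disease-specific baseline score and does not say which score applies when the outcome is general health, ejaculation or anxiety.

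The covariates raise a related, smaller issue. Weight, and so BMI, is first recorded at 8 months and may be a post-treatment value. A man who returns only the 12-month survey has neither Charlson nor BMI, and Section 8 gives no rule for missing covariates.

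**Working it through.** No figure in the plan needs reproducing. The check compares the endpoint list and the Schedule with the three surveys in Appendix A, item by item. One line is counted per question and one per grid row.

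| Items | Baseline | 8 months | 12 months |
|---|---|---|---|
| EPIC-type: urinary 9 + bowel 6 + sexual 6 + mood, energy, weight change 3 | 24 (Q8–20) | 24 (Q17–23, Q25–29, Q34) | 24 (Q19–25, Q27–31, Q36) |
| Health today: five dimensions + 0–100 scale | 0 | 6 (Q35–40) | 6 (Q13–18) |
| Ejaculation | 0 | 4 (Q30–33) | 4 (Q32–35) |
| Prostate cancer and PSA anxiety block | 0 | 0 | 11 + 3 = 14 (Q40–41) |
| The same block plus four cancer-worry statements | 0 | 4 (Q44a–d) | 14 + 4 = 18 (Q40–42) |
| Comorbidity, height, weight | 0 | 3 (Q2–4) | 0 |

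**Endpoints.** Seven are listed and four are change scores. Of those four, EPIC-26 has baseline items and three do not. That is 3 of 4 change endpoints and 3 of 7 primary endpoints.

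**Could the baseline form be incomplete in the text?** Its questions run from 1 to 27 without a gap. Besides the EPIC-type items it holds dates, PSA (Q5–6), treatment plans (Q7), demographics (Q21–27) and one general-health item (Q4). The only mention of weight is Q20c, which asks how much of a problem weight change was.

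**MAX-PC at 8 months.** Appendix A labels no instrument, so the mapping is conditional. If MAX-PC is the Q40–41 block, 0 of 14 items are asked at 8 months. If it also includes the cancer-worry statements, 4 of 18 are. Three further PSA statements (Q7 at 8 months, Q4 at 12) would raise the follow-up counts to 7 and 21. On every reading the baseline count is zero.

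**Ejaculation.** Two of the four items (strength and volume) are rated against how things used to be. That is recall within a follow-up item and does not supply a baseline score.

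**Other sources.** Section 3.2 states "The registry variables to be linked to the cases will include: patient demographic data" and goes on to tumor and treatment data. It lists no patient-reported outcome, comorbidity, height or weight. Medical records are named for recurrence ("Assessment of Cancer Recurrence at 8 Months & 12 Months following Treatment by Patient Medical Records"), but the authorization is requested at the end of the 8-month survey and covers only prostate cancer and its treatment.

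**Covariates.** The Schedule has 3 rows × 3 visits = 9 marks for Charlson, height and weight. Three are delivered, all at 8 months. The history checklist and adult height are reasonable stand-ins for pre-treatment status; weight is less safe.

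**Scale of missing covariates (illustration only).** Section 8 plans 300 + 280 + 288 + 316 + 333 = 1,517 men, or 1,517 − 300 = 1,217 without active surveillance. The documents do not give the share returning only the 12-month survey. Assuming 5–15%:

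- GEE, no Charlson: 0.05 × 1,517 = 76 to 0.15 × 1,517 = 228 men.
- Adverse-event model, no Charlson or BMI: 0.05 × 1,217 = 61 to 0.15 × 1,217 = 183 men.

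**The case against.** The strongest reply is that little of the analysis breaks. The GEE models follow-up scores and needs no change score. Section 8 names EPIC-26 sexual function as the main HRQOL endpoint, and that has its baseline. The hypothesis "PGA is associated with better overall quality of life at 12 months compared to AS" is worded as a 12-month level, so it remains testable, and Section 1.2 has no hypothesis on ejaculation or anxiety. If wording alone resolves the point, it could be called minor.

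All of those facts stand and they limit the consequence. They do not remove the contradiction: three endpoints designated primary cannot be produced as written, and Section 8 leaves their baseline adjustment undefined.

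Some narrower objections also have force:

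- The 5–15% share has no anchor in the documents, and 1,517 may already be net of non-response. The resulting counts carry no weight in the conclusion.
- Men who return only the 12-month survey also miss the graded symptom questions (8-month Q11), so covariates are not all they lack in the adverse-event analysis.
- The 12-month survey text ends at Q42 without a closing page, so a later height, weight or comorbidity item cannot be fully excluded. Its general section has none, and the baseline finding is unaffected.
- Other Schedule rows are not delivered by the surveys as given either: family history at baseline, employment at follow-up, and medications at every visit.

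**Conclusion.** The concern holds. Change from baseline cannot be computed for EQ-5D-5L, MSHQ-EjD or MAX-PC, which is 3 of the 7 primary endpoints. On the narrower reading, MAX-PC exists only at 12 months. The objective of measuring overall quality of life before treatment rests on a single general-health item. Charlson and BMI enter the models as 8-month values, with nothing said about missing ones.

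EPIC-26 and comparisons of follow-up levels are unaffected. No size of residual bias is claimed, because the documents give nothing from which to derive it.

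The conclusion assumes that Appendix A is the full set of instruments, as Section 3.2 indicates. It must be settled before analysis because primary endpoints are wrong as written, even though the repair is cheap.

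**What to change.** **Lead fix, which needs no survey to be open.** Reconcile Sections 1, 1.1, 6.1 and 8 with Appendix A.

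1. For EQ-5D-5L, MSHQ-EjD and MAX-PC, drop the change-from-baseline wording. Define each as an adjusted between-group difference in level at 8 and 12 months, with the Q40–41 anxiety block at 12 months only. Label the instruments in Appendix A. Restate the Section 1.1 objective so that pre-treatment measurement covers what the baseline form collects.
2. In Section 8, name the covariates for these outcomes: baseline EPIC-type domain scores plus general health (Q4), with men already treated at baseline flagged from the Q7 start dates.
3. Correct the Schedule. Baseline patient reported outcomes are the EPIC-type items and Q4; Charlson, height and weight are collected at 8 months only. Check the family history, employment and medication rows at the same time.
4. State that Charlson and BMI are 8-month measurements, give a missing-covariate rule (for example multiple imputation), and repeat the adverse-event model without BMI as a sensitivity analysis.

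This costs protocol and SAP wording only. The three outcomes still lack their own baseline, and EPIC-type scores plus Q4 are a partial substitute.

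**Only if surveys are still open.** Ask comorbidity, height and weight as of before diagnosis in the Baseline Survey or, failing that, in the 12-month survey. Optionally add the 6 health and 4 ejaculation items at baseline and Q40–41 at 8 months. Keep the follow-up recall windows (today for health, past week for Q40, ever for Q41) and use Q7 to flag men already treated. The two ejaculation items rated against the past should still be reported as levels.

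These changes need an IRB amendment and add burden:

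- Baseline now: 22 single questions + 15 + 5 + 5 + 2 + 3 grid rows = 52 lines. The covariates add 3 (55 lines, 3/52 = 6%). With the health and ejaculation items the addition is 13 (65 lines, 13/52 = 25%).
- 8-month survey now: 36 single questions + 56 grid rows = 92 lines. Q40–41 add 14 (106 lines, 14/92 = 15%).

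Enrolment requires that a man "agree to participate by completing the baseline questionnaire", so a longer form could reduce it. Men enrolled before the change would still lack these baselines.

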## 6. Study Procedures

### 6.1 Schedule of Trial Events

Data elements	Baseline	8 months	12 months
Patient reported			
Income	X		
Education	X		
Family history of prostate cancer	X		
Employment status	X	X	X
Charlson co-morbidity	X	X	X
Height	X	X	X
Weight	X	X	X
Medications	X	X	X
Treatment (confirm PGA and SBRT)			
Cancer recurrence		X	X
Secondary treatment(s)		X	X
Adverse events		X	X
Patient reported outcomes	X	X	X
Registry reported			
Age	X		
Race	X		
Marital status	X		
Insurance type	X		
Poverty level based on census tract	X		
PSA	X		
Biopsy pathology	X		
Clinical stage	X		
Treatment	X		

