### **Views Surrounding Impact of Prostate Cancer and Treatment Decision**

41. During the past four weeks, how much of the time have you wished that you could change your mind about the kind of treatment you chose for your prostate cancer?

- All of the time
- Most of the time
- A good bit of the time
- Some of the time
- A little bit of the time
- None of the time

42. How true or false has the following statement been for you during the past four weeks:

I feel that I would be better off if I had chosen the other treatment for prostate cancer.

- Definitely true
- Mostly true
- Neither true nor false
- Mostly false
- Definitely false

43. How true or false has the following statement been for you during the past four weeks:

It bothers me that other men with prostate cancer get treatment that is very different from what I have received.

- Definitely true
- Mostly true
- Neither true nor false
- Mostly false
- Definitely false

44. Listed below are a number of statements concerning a person's beliefs about their own health. During the past week, please indicate how much you agree or disagree with each statement.

	Strongly agree	Agree	Disagree	Strongly Disagree
a. Because cancer is unpredictable, I feel I cannot plan for the future.				
b. My fear of having my cancer getting worse gets in the way of enjoying life.				
c. I am afraid of my cancer getting worse.				
d. I am more nervous since I was diagnosed with prostate cancer.				

**45. Outlook:** How true is each of the following statements for you? (Choose one response on each line)

	Not at all	A little bit	Somewhat	Quite a bit	Very much
a. I feel that my cancer has given me a better outlook on life.					
b. I feel that coping with cancer has made me a stronger person.					

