### **Concerns Surrounding Impact of Prostate Cancer**

Below is a list of comments made by men about prostate cancer and prostate specific antigen (PSA) tests.

40. Please indicate how frequently these comments were true for you **during the past week**. (Choose one for each item)

	Not at all	Rarely	Sometimes	Often
a. Any reference to prostate cancer brought up strong feelings in me.				
b. Even though it's a good idea, I found that getting a PSA test scared me.				
c. Whenever I heard about a friend or public figure with prostate cancer, I got more anxious about my having prostate cancer				
d. When I thought about having a PSA test, I got more anxious about my having prostate cancer.				
e. Other things kept making me think about prostate cancer.				
f. I felt kind of numb when I thought about prostate cancer.				
g. I thought about prostate cancer even though I didn't mean to.				

- h. I had a lot of feelings about prostate cancer, but I didn't want to deal with them.
- i. I had more trouble falling asleep because I couldn't get thoughts of prostate cancer out of my mind.
- j. I was afraid that the results from my PSA test would show that my disease was getting worse.
- k. Just hearing the words "prostate cancer" scared me.

41. Please indicate how frequently these situations have **EVER** been true for you.

	Not at all	Rarely	Sometimes	Often
a. I have been so anxious about my PSA test that I have thought about delaying it.    				
b. I have been so worried about my PSA test result that I have thought about asking my doctor to repeat it.    				

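### MAX-PC anxiety is a primary endpoint as change from baseline at 8 and 12 months, but 14 of the 18 anxiety items are asked only at 12 months and none at baseline

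*Combined protocol and SAP*

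**What the plan says.** The Primary Endpoints in section 1 (Protocol Summary) include "Change from Baseline in Patient-Reported Anxiety as Measured on MAX-PC at 8 Months & 12 Months following Treatment". Section 3.2 A describes collection: "Follow-up questionnaires at 8 months and 12 months will be sent to enrolled participants to ascertain treatment choice and obtain patient-reported outcomes following treatment". The table in section 6.1 has one row, "Patient reported outcomes", ticked at baseline, 8 months and 12 months, with no split by instrument.

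Section 8 analyses patient-reported outcomes with generalised estimating equations, auto-regressive correlation, a baseline-score covariate and a time-by-treatment interaction. It gives no rule for scoring an incomplete instrument.

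In Appendix A, the Second Follow Up Survey has three consecutive anxiety blocks:

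- Q40 opens "Below is a list of comments made by men about prostate cancer and prostate specific antigen (PSA) tests"; its first item is "Any reference to prostate cancer brought up strong feelings in me".
- Q41 opens "Please indicate how frequently these situations have" ever applied, and asks about PSA tests.
- Q42 opens "Listed below are a number of statements concerning a person's beliefs about their own health" and asks about fear of the cancer worsening.

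The First Follow Up Survey contains the last of these as Q44, with the same items and response options. It has no counterpart of the other two.

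**The concern.** A change-from-baseline endpoint at two follow-up times needs the same instrument on three forms. Here the blocks that look like the anxiety instrument are complete on one form, mostly absent from the second and wholly absent from the third.

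Section 8 allows for a man who misses one survey. It does not allow for items that nobody was asked. Neither a missing-data method nor a larger sample recovers them. For this endpoint there would be no 8-month full score to compare between active surveillance and the treatments, no 8-to-12-month trajectory, and no baseline from which to measure change or to adjust. The last matters particularly in a non-randomised cohort, where anxiety before treatment may influence which treatment a man chooses.

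**Working it through.** The plan states no MAX-PC item count, standard deviation, effect size or power, so there is no figure of its own to reproduce. The check is a count of items by form.

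**Matching forms to times.** There are two follow-up surveys and two follow-up times (section 3.2 A). By order, the first is 8 months and the second is 12 months.

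**Ruling out lost text.** Question numbers run without a gap on all three forms: Baseline 1-27, First Follow Up 1-46, Second Follow Up 1-42. The absence is therefore not an effect of reading the PDF.

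**Count.**

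| Block | Baseline | 8 months | 12 months |
|---|---|---|---|
| Prostate-cancer anxiety (Q40 a-k) | 0 | 0 | 11 |
| PSA-test anxiety (Q41 a-c) | 0 | 0 | 3 |
| Fear of worsening (Q44 / Q42 a-d) | 0 | 4 | 4 |
| Total | 0 | 4 | 18 |

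- 12 months: 11 + 3 + 4 = 18.
- 8 months: 4/18 = 22% present; 14/18 = 78% absent.
- Baseline: 0/18. The nearest item is the depression line in Q20.

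**Sensitivity to the definition.** Three further PSA statements are asked at both follow-ups (Q7 at 8 months, Q4 at 12 months). Counting them gives 4 + 3 = 7 of 18 + 3 = 21, or 33% present at 8 months. The same 14 items are still missing, and the Baseline Survey has none of the 21.

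**Sensitivity to the mapping.** If MAX-PC includes Q40 or Q41, the full score exists only at 12 months. If it were only the four-item block, an 8-month score would exist, but Q40 and Q41 would then serve no listed endpoint and there would still be no baseline. Change from baseline therefore fails at both times on every mapping within these items.

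**By arm.** The only routing on the 8-month form sends men on surveillance or not yet treated past Q11-Q15. All five groups get the same anxiety items.

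**Consequence for the model.** With one follow-up time, neither the time-by-treatment interaction nor the auto-regressive correlation can be estimated. With no baseline, the baseline-score covariate does not exist.

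**Contrast.** The EQ-5D-5L, urinary, bowel, sexual, ejaculation and regret questions all appear on both follow-up forms. The dropped blocks are specific to anxiety, and nothing in the plan says MAX-PC is a 12-month-only measure.

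**The case against.** The strongest reply is that no survey item is labelled MAX-PC and no section gives its items or scoring, so the count of 18 is inferred. That is fair. The finding is therefore conditional on Q40 or Q41 belonging to the instrument, although the absence of a baseline does not depend on that condition. Matching the first follow-up form to 8 months is also inferred, but if the order were reversed, one of the two times would still lack the items.

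A reader might infer three stronger things that the documents do not support.

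- *No anxiety comparison is possible at 8 months.* Q44, the PSA statements in Q7 and the EQ-5D anxiety item (Q40 on that form) are all asked at 8 months and repeated at 12. They allow limited comparisons of level. What is lost is the full score.
- *Scores will shift between forms simply because the item count differs.* That would need a rule to sum whatever was asked, and an assumed item scoring. Section 8 proposes neither, and the blocks use different response formats (frequency in Q40-Q41, agreement in Q42/Q44).
- *The number affected is the total of the group estimates in section 8.* Those are men expected to be evaluated. Surveys go to all enrolled men, planned at 2,378.

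It may also be said that anxiety is peripheral: section 8 names EPIC-26 sexual function as the main HRQOL endpoint, and section 1.2 has no anxiety hypothesis. Those analyses are indeed untouched. MAX-PC is nevertheless one of seven listed primary endpoints and cannot be delivered as defined.

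**Conclusion.** The concern holds as a conflict between a stated primary endpoint and the forms meant to measure it. Of 18 anxiety items at 12 months, 4 are asked at 8 months and none at baseline, in every arm. If MAX-PC includes Q40 or Q41, the full score is available only at 12 months, and the longitudinal model in section 8 has one time point for it. Change from baseline cannot be computed at 8 or at 12 months.

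Repairing the 8-month form alone would not be enough, because the baseline gap would remain. The conclusion rests on two inferences: the mapping of these blocks to MAX-PC, and the matching of forms to times by order. It does not rest on any scoring rule. It should be resolved before analysis.

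**What to change.** State in the protocol which survey items make up MAX-PC and how they are scored. Then:

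1. **Baseline Survey:** insert Q40 a-k, Q41 a-c and the Q42 block (18 items), with the recall period stated as pre-diagnosis or current. Several items presuppose a diagnosis, so that choice has to be made explicitly.
2. **First Follow Up Survey:** insert Q40 a-k and Q41 a-c (14 items), unchanged, before Q44.
3. **Men already surveyed without these items:** restate the endpoint as the between-group MAX-PC level at 12 months, not change from baseline. Drop the baseline-score covariate and the time-by-treatment term for it. Say that the comparison is not adjusted for anxiety before treatment. Report the common Q44/Q42 block at 8 and 12 months under its own name, not as MAX-PC.

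The first two steps add 18 + 14 = 32 tick-box items over two forms: a few minutes of respondent time and an IRB amendment. The third changes endpoint and analysis wording only. It loses the 8-month and change results for the full score, which cannot be recovered from forms already completed.
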